3.8 Preload challenge

The protocol for preload challenge is adapted from the standard international guidelines as recommended by Blundell et al. (2010). The purpose of this preload challenge is to investigate the change in appetite associated with each of the 4 weight-loss intervention diets.

Schedule for the preload challenge visit

The preload challenge will take place at the Appetite Research Centre in HNU. Participants will arrive at HNU at 8:00am after an overnight fast of approximately 10 hours, having consumed nothing but water since the prior evening meal. Upon arrival, the participant will be given a glass of water (250mL) to drink and their anthropometric measurements will be taken, followed by blood pressure.

For all participants, baseline Visual Analogue Scale (VAS) ratings of appetite will be measured at 8:50am (t = 0 min), before the breakfast. At the same time, a 10mL fasting blood sample will also be collected (t = 0 min). At 9:00am participants will be given a preload breakfast and allowed 15 minutes to consume all components of the meal. The meal will be given within an individual dining booth. Participants will rate the palatability of the preload breakfast using standard VAS methods. At specific time points over a period of 3.5 hours (t = 0, 15, 30, 60, 90, 120, 150, 180 and 210 mins), participants will rate appetite-related sensations (hunger, fullness, satisfaction, thoughts of food, thirsty and nausea) using standard VAS methods. At 11:05am, participants will be given a glass of water (250mL) to drink for rehydration. Participants should finish the glass of water within 10 minutes.

A subset of participants who consent for repeat blood sampling will undergo forearm venous cannulation by the Research Nurse. Apart from fasting blood sample being collected (t = 0 min; 10mL blood), blood samples will also be collected intermittently after preload breakfast (t = 15, 30, 60, 90, 120, 150, 180, 210 mins; 7mL blood at each time point). Collectively, a total of 66mL of blood will be collected from these participants on each of the 2 preload study days. The participants will complete the preload challenge study at 12:30pm, and the cannula will be removed.

The summary of the visit schedule for the preload challenge is as follows:

08:15am – 250mL water to drink
08:30am – cannulation
08:50am – VAS, baseline blood sample (t0)
09:00am – preload breakfast
09:15am – VAS, blood sample (t15)
09:30am – VAS, blood sample (t30)
10:00am – VAS, blood sample (t60)
10:30am – VAS, blood sample (t90)
11:00am – VAS, blood sample (t120)
11:05am – 250mL water to drink
11:30am – VAS, blood sample (t150)
12:00pm – VAS, blood sample (t180)
12:30pm – VAS, blood sample (t210)

Preload breakfast

The Cambridge LED meal replacement along with peanut butter toast and egg will be used as the preload breakfast. A glass of 250mL water will also be given to drink for hydration and aid swallowing. The identical preload will be used at Week 0 and Week 8, irrespective of the diet intervention arm. For example the preload may be a 227mL meal replacement shake, which contains approximately 1.8MJ, 29g protein, 39.2g CHO and 16.8g fat. The purpose of using identical preload for all participants at all preload challenge occasions is so that participants will be exposed to the same acute stimuli (i.e. the preload breakfast), and any difference in the appetite response can be expected to be linked to the differences in long-term stimuli (i.e. high-protein vs low-CHO diets).

Visual analogue scales (VAS)

Appetite-related VAS will be used following the international methodology of Blundell et al. (2010). The following questions will be used: “How hungry do you feel? / How full do you feel? / How satisfied do you feel? / How much do you think you can eat now / How nauseous do you feel?” anchored on the left by “I am not hungry at all / I am not full at all / I am completely empty / nothing at all / not nauseous at all” and “I am as hungry as I have ever been / I am totally full / I cannot eat another bite / a large amount / very nauseous” on the right. Participants will mark their responses by placing a vertical line across the 100-mm scale according to their subjective feelings (Fig 1).

Hunger

- How hungry do you feel?
- ANCHOR: 'I am not hungry at all' vs. 'I am as hungry as I have ever been'

Fullness

- How full do you feel?
- ANCHOR: 'I am not full at all' vs. 'I am totally full'

Satisfaction

- How satisfied do you feel?
- ANCHOR: 'I am completely empty' vs. 'I cannot eat another bite'

Thoughts of food

- How much do you think you can eat now
- ANCHOR: 'nothing at all' vs. 'a large amount'

Thirst

- How thirsty do you feel?
- ANCHOR: 'I am not thirsty at all' vs. 'I am as thirsty as I have ever been'

Nausea

- How nauseated do you feel?
- ANCHOR: 'I do not feel nauseated at all' vs. 'I am as nauseated as I have ever been'

[figure not shown]

Figure 1. Example of VAS.

Following the preload breakfast participants will also rate pleasantness, visual appeal, smell, taste, aftertaste and overall palatability using VAS.

Pleasantness

- How pleasant was the meal?
- ANCHOR: 'not at all pleasant' vs. 'as pleasant as I have ever tasted'

Appearance

- How did the meal look?
- ANCHOR: 'good' vs. 'bad'

Smell

- How did the meal smell?
- ANCHOR: 'good' vs. 'bad'

Taste

- How did the meal taste?
- ANCHOR: 'good' vs. 'bad'

Aftertaste

- How much aftertaste was there?
- ANCHOR: 'much' vs. 'none'

Palatability

- How appealing was the meal?
- ANCHOR: 'good' vs. 'bad'

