3.2 Low Energy Diet (LED)

Commercial LED meal replacements (Cambridge Weight Plan™ Ltd) will be provided to participants at no cost to provide the base energy and macronutrient content of their daily diet. The LEDs offer a range of products, including shakes, soups, bars, porridge, pasta and savoury meals, which in turn are comprised of different macronutrient composition. Therefore, participants in different intervention arms will receive products with macronutrient composition that will align with the intervention arm (Table 2). Participants must consume the LED meal replacements throughout the 8-week weight loss period.

Participants will be recommended to have a total of 4 eating occasions every day, which will consist of 1 fixed oat breakfast, 2 fixed commercial LED meal replacements (participants must adhere to the recommended intake, $\approx 1.7\text{MJ/day}$) and 1 variable home meal (participants may eat less if not hungry or eat a little more if needed). An example for the recommended fixed and variable meals is shown in Table 3. The recommended total daily energy intake is either 3.9MJ or 4.6MJ, depending on the participants' energy requirement.

Table 3. Recommended eating occasions and meal format in a day.

Eating occasions	Meal format	Comment
Breakfast	Fixed – oat breakfast	To prepare and consume the oat breakfast completely
Lunch	Fixed – meal replacement	To consume meal replacements completely.
Afternoon Tea	Fixed – meal replacement	
Dinner	Variable – home prepared meal	To consume additional food items to meet the absolute protein (g/kg/day) and overall macronutrient composition (en%) targets.

Participants will buy the ingredients to prepare oat breakfasts and home prepared meals. They will be given oral and written instructions on how to prepare this breakfast. Participants must consume the oat breakfast completely. In addition, the participants will consume 2 fixed LED meal replacements every day as lunch and afternoon tea. Following that, participants will be advised to prepare and consume a variable home meal, comprising high/normal protein in combination with normal/low CHO each day, in order to achieve the differential macronutrient composition of the 4 intervention diets. A diet plan booklet containing various food items and portion sizes, specific for each intervention arm, will be given to participants to help the preparation of the variable home meal. The food items used to achieve protein,

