At CID1 (Week 0), the visit will take approximately 5 hours. Participants are required to arrive at HNU at 8am for a preload challenge (see Section 3.7). After the preload challenge, participants will be given a lunch meal. Participants are also required to complete a 3-factor eating questionnaire (3FEQ) and a Baecke Questionnaire. It will be followed by a dietary consultation session with an investigator. Finally, participants will be invited to the Auckland City Hospital to perform a body composition scan using DXA (see Section 3.9). The 8-week weight loss intervention period will be commenced after CID1, whereby participants are required to adhere to their assigned intervention diets (HPNC/HPLC/NPNC/NPLC). The intervention comes to the end upon the completion of CID3.

At CID 2 (Week 4), the visit will take approximately 30 minutes. Participants are required to arrive in the morning at any time between 8:00am and 11:00am for their anthropometric measurements to be taken, following by blood pressure. Then a Research Nurse will collect 7mL of fasting blood. Finally, there will be a dietary consultation session with an investigator.

At CID 3 (Week 8), the visit itinerary will be the same as CID 1. The study is completed upon the end of CID 3 visit.

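### An identical breakfast alone cannot separate the last arm-specific dinner from 8 weeks of diet, so attributing week-8 appetite differences to long-term stimuli is not established by this design

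*Protocol*

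**What the plan says.** Section 3.8 (Preload challenge) holds the test breakfast constant: "The identical preload will be used at Week 0 and Week 8, irrespective of the diet intervention arm". The reason given is that "participants will be exposed to the same acute stimuli (i.e. the preload breakfast"), from which the protocol concludes that "any difference in the appetite response can be expected to be linked to the differences in long-term stimuli". The breakfast is the only acute stimulus it names.

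The only control on earlier intake is the fast: participants arrive at 8:00am "after an overnight fast of approximately 10 hours, having consumed nothing but water since the prior evening meal". Neither 3.7 nor 3.8 says what that evening meal should be or when it should end.

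Section 3.7 (Clinic visits) sets the limits of the diet. At the start, "The 8-week weight loss intervention period will be commenced after CID1". At the end, "The intervention comes to the end upon the completion of CID3".

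Section 3.2 makes dinner the variable, home-prepared meal. Table 3 describes its role as "To consume additional food items to meet the absolute protein (g/kg/day) and overall macronutrient composition (en%) targets", and the accompanying text lets its size vary with hunger and fullness.

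**The concern.** Standardising the breakfast is meant to leave the long-term diet as the only difference between arms. It leaves two differences: what the woman has eaten for 8 weeks, and what she ate the evening before. At week 8 both are set by her arm. The week-0 challenge cannot remove the second, because the dinner before it precedes the intervention.

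The distinction matters to this trial. Section 1.3 treats the short-term effect of a higher-protein meal on appetite biomarkers as settled and the long-term evidence as limited. Section 1.4 discusses plasma amino acids as a possible appetite signal, and section 3.12 lists amino acids, insulin and gut peptides among the fasting and postprandial measurements. If the previous dinner leaves any trace in these or in the appetite ratings, a week-8 difference could be reported as sustained adaptation when part of it reflects one recent meal. The outcomes affected are the first two secondary outcomes in section 3.11: appetite biomarkers and VAS ratings.

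**Working it through.** The protocol states no figure for this point, so there is none to reproduce. The check has four steps.

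**1. Which meal precedes each challenge**

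| | Week 0 (CID1) | Week 8 (CID3) |
|---|---|---|
| Diet in force the evening before (3.7) | Not yet started | Assigned diet |
| Evening meal (3.2) | Participant's own | Arm-specific, ad lib dinner |
| Common evening meal specified (3.7, 3.8) | No | No |
| Breakfast (3.8) | Identical | Identical |

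At week 8, arm determines both the type of last dinner and the preceding 8 weeks of diet. No contrast in the design varies one while holding the other fixed.

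**2. Interval from dinner to challenge**

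Inputs from 3.8: a fast of about 10 h at the 8:00am arrival, first rating and blood sample at 8:50am, preload at 9:00am, last rating at 12:30pm.

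- End of dinner: 8:00am − 10 h = 10:00pm.
- To the first rating: 10 h + 50 min ≈ 10.8 h.
- To the preload: 10 + 1 = 11 h.
- To the last rating: 10 + 4.5 = 14.5 h.

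If the actual fast is 9 to 12 h (an assumed range), dinner to preload is 10 to 13 h.

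**3. Daily contrast between arms (Appendix 1)**

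| | 3.9 MJ plan | 4.6 MJ plan |
|---|---|---|
| Protein, HP − NP | 118 − 81 = 37 g | 138 − 96 = 42 g |
| CHO, NC − LC | 95 − 65 = 30 g | 110 − 77 = 33 g |
| Fat, NPLC − HPNC | 40 − 11 = 29 g | 46 − 12 = 34 g |

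These are whole-day differences. Section 3.2 uses dinner to create the contrast, but it also says the meal-replacement products are matched to the arm, so dinner may carry less than the full amount. As an upper bound, if the fixed meals were equal across arms, the whole 37 to 42 g of protein would fall at dinner. That would exceed the 29 g in the example preload.

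**4. What a carry-over would do, for illustration only**

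The documents give no carry-over size, so the shift d below (in SD units) is assumed. Completers per protein level, using the recruitment target and dropout rate in 3.5: 140 × 0.9 / 2 = 63. For a two-sided 5% comparison of two means with no true long-term effect, the noncentrality is d × √(63/2) = 5.61d. The rejection probability (normal approximation) is Φ(5.61d − 1.96) + Φ(−5.61d − 1.96).

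| d (SD) | 5.61d | Probability of a significant result |
|---|---|---|
| 0.05 | 0.28 | 6% |
| 0.1 | 0.56 | 9% |
| 0.2 | 1.12 | 20% |
| 0.3 | 1.68 | 39% |
| 0.4 | 2.24 | 61% |

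This applies only to VAS ratings and fasting samples, which all participants provide. Postprandial blood comes from a consenting subset of unstated size. With an assumed 20 per level, the factor is √(20/2) = 3.16, and shifts of 0.2, 0.3 and 0.4 SD give about 10%, 16% and 24%.

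**The case against.** The strongest reply is that the last dinner is part of the treatment. The protocol glosses its long-term stimuli as the diets themselves, and 3.8 gives the purpose of the challenge as studying appetite change associated with each of the four diets. For that purpose randomisation gives a valid comparison and the dinner is not a confounder. This stands. A reader might infer that the appetite comparison between arms is biased or invalid, and the documents do not support that. What is unsupported is the narrower step of assigning differences to long-term exposure because the breakfast was identical.

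Second, the overnight fast is a washout of about 11 h before the preload, and nothing in the documents shows that an effect survives it. This also stands. A reader might infer that carry-over is known to occur or to be large, but the documents give no figure, and at 0.05 to 0.1 SD the error rate is close to nominal. The sentence is hedged as well, so the right criticism is that its claim is not established, not that it is false.

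Third, every arm moves from its own dinner to a plan dinner between week 0 and week 8. That general shift affects within-arm change and does not by itself favour any arm.

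Fourth, a common dinner has its own drawback: it departs from each assigned diet by a different amount just before the final visit. This is a real trade-off, but it makes the last meal equal across arms, which is the protocol's own reason for a common breakfast.

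**Conclusion.** The point holds in limited form. The evening meal before the week-8 challenge is arm-specific and ad lib, the one before week 0 is not, and neither is standardised. The identical breakfast therefore cannot distinguish an effect of the most recent meal from adaptation to 8 weeks of diet, and the attribution in 3.8 is not established by the design.

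The size of any carry-over is unknown and may be small. The 37 to 42 g protein gap is a daily figure and only an upper bound for dinner. The rejection probabilities rest on assumed shifts. The comparison remains valid for appetite change under each assigned diet including its most recent meal, and the primary analysis of body weight is not in question. The change is worth making before data collection, because afterwards the only remedy is a weaker claim.

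**What to change.** In 3.7 and 3.8, specify one common evening meal with a fixed finishing time for all arms before both CID1 and CID3. A single meal-replacement product already supplied by the study would be one example. Schedule the 24-hour urine and food-record days, which 3.7 places in the week before these visits, so that they avoid that evening.

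The cost is two standard meals per participant and one line in the visit instructions. The downside is that one dinner in 8 weeks, the one before CID3, is not arm-specific.

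If the common meal is not adopted, reword the sentence under Preload breakfast in 3.8 so that week-8 differences are attributed to the assigned diet including its most recent meal. That costs one sentence, but the trial then makes no claim to have isolated long-term adaptation.

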3.9 Group meetings

In addition to the clinic visits described above, there will also be group meetings at Week 0, Week 2, Week 4 and Week 6 to provide behavioural counselling and also provide participants with general knowledge to overcome any difficulties they face during the weight loss intervention. This is also aimed to promote adherence to the intervention. The group meetings will be led by a trained health professional, supported by a postgraduate nutrition & dietetics research student. Participants will attend different meetings according to the intervention arms wherever possible. Each group meeting will take approximately one hour.

3.9 Compliance

Compliance to the diet arms will be monitored using a 24-hour urinary nitrogen assessment and 4-day food records. Investigators will contact participants through phone calls to inquire about their dietary progress and promote compliance throughout the 8-week intervention. Participants may also contact the investigators if they require any dietary or other advice between group visits.

3.10 Dual Energy X-Ray Absorptiometry (DXA)

DXA body composition measurement will take place at Department of Surgery Body Composition Unit at Auckland City Hospital. DXA is based on the 3 component model of body composition, and uses 2 x-ray energies to measure body fat mass, lean mass, and bone mineral density. A rapid scan iDXA (GE-Lunar, Madison, WI) designed to allow scanning of larger individuals with high body weight and BMI will be used. The participant is required to lie recumbent on the open scanner bed for approximately 10 minutes. Body composition comprising total body fat, fat-free soft tissue and bone mineral content as well as regional fat deposition will be determined from DXA whole-body and segmental scans. DXA scans are a low-risk research tool, commonly used in nutrition intervention trials. A single scan provides exposure similar to that of a 1 hour flight between Auckland and Wellington.

3.11 Outcome variables

Primary outcome

- i. Change in body weight.

Secondary outcome

- i. Plasma concentration of appetite-related biomarkers.
- ii. VAS ratings for appetite sensations following a preload breakfast challenge.
- iii. Change in body composition (fat mass and fat-free mass).

Other

- i. Other metabolic parameters and urinary nitrogen.
- ii. 4-day food records.

3.12 Blood and urine parameters

Fasting blood samples

- i. Hb_{A1c}
- ii. Glucose (FPG)
- iii. Cholesterol (total-C, LDL-C, HDL-C) and triglyceride
- iv. Liver function (AST, ALT, ALP, GGT)
- v. CCK, GLP-1, PYY, GIP, insulin, C-peptide, glucagon and amylin
- vi. Amino acids

Postprandial blood samples (a subset of participants during preload-test meal challenge only)

- i. Glucose
- ii. CCK, GLP-1, PYY, GIP, insulin, C-peptide, glucagon and amylin
- iii. Amino acids

Urine parameters (for the assessment of protein intake compliance)

- i. Urine nitrogen

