3.1 Trial Design

This trial is conducted as a 4-arm parallel intervention study, comparing 4 different weight loss LEDs based on a 2 x 2 factorial design. The study will comprise 2 higher-protein diet treatments and 2 lower-CHO diet treatments.

Table 1. Four treatments in the study.

Components	High-Protein (HP)	Normal-Protein (NP)
Normal-CHO (NC)	HPNC	NPNC
Low-CHO (LC)	HPLC	NPLC

Each eligible participant will be randomised to one of the 4 intervention arms and will need to adhere to the assigned diets for 8 weeks. The target daily energy intake during the 8-week weight-loss period is approximately 40% of their daily energy requirement at the time of screening, calculated using the Harris-Benedict's Equation and participants will be assigned to the nearest 3.9 or 4.6MJ diet plan. An LED will be used in part to achieve this dietary target.

HP diet (50en%) is aimed to provide 1.2g/kg/day protein; whereas NP diet (35en%) is aimed to provide 0.8g/kg/day protein. Conversely, the LC arm is aimed to provide 28en% CHO; whereas the NC arm is aimed to provide 40en% CHO. The balance of energy for each diet treatment will comprise dietary lipid. The macronutrient composition of each diet during the weight-loss period is shown in Table 2; whereas the absolute intake of macronutrients (grams) for each intervention is shown in Appendix 1. Throughout the intervention period, participants are asked to maintain their usual physical activity level.

Table 2. Macronutrient composition of the intervention diets.

High-Protein (HP)		Normal-Protein (NP)	
Normal-CHO (NC)	Low- CHO (LC)	Normal- CHO (NC)	Low- CHO (LC)
50en% Protein	50en% Protein	35en% Protein	35en% Protein
40en% CHO	28en% CHO	40en% CHO	28en% CHO
10en% Fat	22en% Fat	25en% Fat	38en% Fat

en%, percentage of energy

Investigators will explain the macronutrient composition of the diet to participants either individually or as a group of participants who are assigned to the same intervention arm.

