3.7 Clinic visits

The summary of the screening and clinical investigation days (CIDs) are shown in Table 5. Participants are required to attend all visits.

Table 5. Agenda during each visit at HNU.

Agenda	Screening	Baseline	8-week weight loss	
		CID 1 Week 0	CID 2 Week 4	CID 3 Week 8
Informed consent	✓			
Anthropometric measurement ¹	✓	✓	✓	✓
Blood pressure	✓	✓	✓	✓
Fasting blood sample	✓	✓	✓	✓
24-hour urine		✓	✓	✓
4-day food record		✓	✓	✓
DXA		✓		✓
Preload challenge		✓		✓
3-factor eating questionnaire		✓		✓
Baecke Questionnaire		✓		✓
Dietary consultation		✓	✓	✓

¹ Anthropometric measurements include body weight, body height and waist/hip circumference.

Screening visit

During the screening visit, participants are required to arrive at HNU after an overnight fast of at least 10 hours, having consumed nothing but water since the prior evening meal.

Participants will receive a Participant Information Sheet (PIS) and the study will be explained by a researcher. Participants will be given the opportunity to ask questions and written informed consent will be obtained. Participants will then be screened for eligibility. Demographics (age and ethnicity) and anthropometry (height, body weight, waist and hip circumference, BMI and blood pressure) will be recorded. A venous blood sample will be collected to check for fasting plasma glucose (FPG) concentration on site to screen for diabetes. When FPG is ≥ 7.0 mmol/L, another venous blood sample will be collected to check for HbA1c. When HbA1c ≥ 50 mmol/L, participant's GP will be contacted to confirm whether the participant has diabetes.

After confirming the participant's eligibility, participants will be given a urine bottle, alongside verbal and written instruction on how to collect urine samples. Additionally, participants will be taught to complete a 4-day food record (3 weekdays and 1 weekend) by investigators. Participants are asked to collect the urine sample on one of the days of the food record. The urine samples and 4-day food records will be completed during the week before attending CID1 and CID 3.

Clinical Investigation Days (CIDs)

For all CIDs, participants are required to arrive at HNU after an overnight fast of approximately 10 hours, having consumed nothing but water since the prior evening meal.

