Appendix 1 Absolute macronutrient intake (grams) for each intervention.

(a) 3.9 MJ meal plan

Intervention arm	HPNC 50/40/10en%	HPLC 50/28/22en%	NPNC 35/40/25en%	NPLC 35/28/38en%
Protein	118g	118g	81g	81g
CHO	95g	65g	95g	65g
Fat	11g	23g	26g	40g

(b) 4.6MJ meal plan

Intervention arm	HPNC 50/40/10en%	HPLC 50/28/22en%	NPNC 35/40/25en%	NPLC 35/28/38en%
Protein	138g	138g	96g	96g
CHO	110g	77g	110g	77g
Fat	12g	27g	31g	46g

References:

- BHOGAL, M. S. & LANGFORD, R. 2014. Gender differences in weight loss; evidence from a NHS weight management service. *Public Health*, vol 128 issue 9, pp 811-813.
- BILSBOROUGH, S. & MANN, N. 2006. A review of issues of dietary protein intake in humans. *Int J Sport Nutr Exerc Metab*, 16, 129-52.
- BOSSE, J. D. & DIXON, B. M. 2012. Dietary protein in weight management: a review proposing protein spread and change theories. *Nutr Metab (Lond)*, 9, 81.
- BRENNAN, I. M., LUSCOMBE-MARSH, N. D., SEIMON, R. V., OTTO, B., HOROWITZ, M., et al. 2012. Effects of fat, protein, and carbohydrate and protein load on appetite, plasma cholecystokinin, peptide YY, and ghrelin, and energy intake in lean and obese men. *Am J Physiol Gastrointest Liver Physiol*, 303, G129-40.
- CHUNGCHUNLAM, S. M., HENARE, S. J., GANESH, S. & MOUGHAN, P. J. 2015. Dietary whey protein influences plasma satiety-related hormones and plasma amino acids in normal-weight adult women. *Eur J Clin Nutr*, 69, 179-86.
- CLIFTON, P. M., CONDO, D. & KEOGH, J. B. 2014. Long term weight maintenance after advice to consume low carbohydrate, higher protein diets--a systematic review and meta analysis. *Nutr Metab Cardiovasc Dis*, 24, 224-35.

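### The urine that checks protein intake is assayed for nitrogen alone, so a low value cannot be told apart from an incomplete collection

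*Protocol*

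**What the plan says.** The compliance section (3.9) names two tools: "Compliance to the diet arms will be monitored using a 24-hour urinary nitrogen assessment and 4-day food records". Section 3.12 (Blood and urine parameters) gives the purpose of the urine, "Urine parameters (for the assessment of protein intake compliance", and lists one analyte, "Urine nitrogen".

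Collection is in the participant's hands. Under Clinic visits (3.7), "participants will be given a urine bottle, alongside verbal and written instruction on how to collect urine samples". There is one sample per time point: "Participants are asked to collect the urine sample on one of the days of the food record". The text places collections before two visits: "The urine samples and 4-day food records will be completed during the week before attending CID1 and CID 3". Table 5 also ticks a 24-hour urine at Week 4.

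The contrast to be verified is set in Section 3.1: "HP diet (50en%) is aimed to provide 1.2g/kg/day protein; whereas NP diet (35en%) is aimed to provide 0.8g/kg/day protein". Appendix 1 ("Absolute macronutrient intake (grams) for each intervention") turns it into 118 g against 81 g of protein on the 3.9 MJ plan, and 138 g against 96 g on the 4.6 MJ plan.

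The protocol states no completeness marker, start or stop time, missed-void question or rule for an incomplete collection. Plasma amino acids are measured, but as appetite-related biomarkers and not to check compliance.

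**The concern.** Total 24-hour nitrogen is concentration times collected volume, so each missed void lowers the estimate of protein intake. With nitrogen as the only analyte, a low result has two explanations, a diet low in protein or a collection that is short, and the sample cannot separate them. The food record for the same day helps only in part, because it is self-reported.

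This matters because protein intake is free to vary. Section 3.2 lets women eat more or less of a home-prepared dinner, and that meal is the one meant to bring them to their protein target. Section 1.5 also says that success depends on the protein difference between groups and on each person's change from baseline. Urinary nitrogen is the only objective evidence on either.

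The choice belongs in the protocol. An analysis plan can set rules for the data, but it cannot supply a marker that was never assayed.

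**Working it through.** HP and NP mean high- and normal-protein.

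**1. Reproduce the targets.** Protein (g) = energy x protein share / energy per gram, taking 16.7 to 17 kJ/g (assumption).

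- 3.9 MJ, HP: 1950 kJ gives 114.7 to 116.8 g (stated 118). NP: 1365 kJ gives 80.3 to 81.7 g (stated 81).
- 4.6 MJ, HP: 2300 kJ gives 135.3 to 137.7 g (stated 138). NP: 1610 kJ gives 94.7 to 96.4 g (stated 96).

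The stated grams agree with the plan to within rounding of a few grams, and they are used below.

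**2. Loss that hides the contrast, with urinary nitrogen proportional to intake.** A complier in the HP arm reads as NP when the missing fraction is 1 - NP/HP. She reads at the midpoint of the two targets at half that fraction.

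- 3.9 MJ: 1 - 81/118 = 31.4%; midpoint 15.7%.
- 4.6 MJ: 1 - 96/138 = 30.4%; midpoint 15.2%.
- Per-kg targets: 1 - 0.8/1.2 = 33.3%; midpoint 16.7%.

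Smaller losses do less. On 3.9 MJ, 10% missing gives 118 x 0.90 = 106 g, still nearer 118 than 81. At 20% missing she reads 94 g, and 23.6/37 = 64% of the gap is gone.

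**3. Other nitrogen assumptions.** Intake nitrogen = protein/6.25. A fixed 2 g or 4 g is taken off for non-urinary loss, or a net 1 g is added (3 g from body protein less 2 g). All are assumptions.

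| Urinary nitrogen | 3.9 MJ HP/NP (g) | Midpoint | Equal | 4.6 MJ HP/NP (g) | Midpoint | Equal |
|---|---|---|---|---|---|---|
| Intake | 18.88/12.96 | 15.7% | 31.4% | 22.08/15.36 | 15.2% | 30.4% |
| Intake - 2 g | 16.88/10.96 | 17.5% | 35.1% | 20.08/13.36 | 16.7% | 33.5% |
| Intake - 4 g | 14.88/8.96 | 19.9% | 39.8% | 18.08/11.36 | 18.6% | 37.2% |
| Intake + 1 g | 19.88/13.96 | 14.9% | 29.8% | 23.08/16.36 | 14.6% | 29.1% |

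The range is 15-20% for the midpoint and 29-40% for equality.

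**4. In voids.** If voids are equal and number 5 to 8 a day (assumption), one missed void is 12.5-20% of the urine and two are 25-40%.

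**5. Change from baseline.** Section 1.5 cites an intake about 40% above baseline. With a complete baseline sample and proportional nitrogen, a true 40% rise reads as 1.4 x 0.85 = 1.19 with 15% of the later urine missing. With 30% missing it reads as 1.4 x 0.70 = 0.98, no rise at all.

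**6. Loss shared by all arms (3.9 MJ).** One void in six missing everywhere gives 98.3 against 67.5 g. The difference is 30.8 g, or 83% of the planned 37 g. At 30% missing everywhere, the values are 82.6 against 56.7 g, a difference of 25.9 g, or 70%. The ratio of the arms does not change.

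**The case against.** Three stronger readings are tempting, and the documents support none of them.

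- *Ordinary under-collection makes an HP woman look NP.* No under-collection rate is given. Equality needs roughly a third of the day's urine to be missing, and at 10% she is still nearer the HP target.
- *A null weight result could not be interpreted.* Whether the arms differed in protein is a question about group means, with 35 women per arm and 70 per protein level. Random collection errors average out, and shared loss leaves most of the contrast visible. Nothing in the protocol suggests that one arm would lose more urine than another. Section 3.11 lists urinary nitrogen under Other, outside the primary body-weight comparison.
- *Compliers would be classed as non-compliant.* The protocol monitors compliance. It sets no nitrogen cut-off, compliance class or exclusion based on urine.

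It can also be said that a 24-hour total already needs a measured volume, that the collection instructions are not shown, and that rejection rules often sit in a laboratory procedure or analysis plan. Each woman also has a baseline collection and at least one on diet.

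All of this limits the consequence. It does not close the gap: the assay list is fixed in the protocol, volume alone does not show completeness, and a baseline sample of unknown completeness cannot settle whether a later one is short.

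**Conclusion.** The point holds as a minor one. The sole objective check of protein intake cannot distinguish low intake from a short collection. About 15-16% missing makes a compliant HP woman ambiguous and about 30-31% makes her read as NP, if nitrogen is proportional to intake; the wider ranges are 15-20% and 29-40%. How often losses of that size occur is an assumption that the documents do not inform.

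Two things are harmed: the reading for an individual woman, including her change from baseline, and the estimated size of the protein separation, which shared loss understates in proportion. The randomised comparison of body weight is not biased.

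**What to change.** In Section 3.12, add urinary creatinine on the same sample. Record total volume, start and stop times and missed voids on the collection form.

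Set beforehand a rule for an incomplete collection. It could compare creatinine with the same woman's other collections, or use creatinine per kg of DXA lean mass at Weeks 0 and 8. DXA is not done at Week 4, so any collection then needs the within-woman comparison. The text and Table 5 should also be reconciled on whether a Week 4 urine is collected.

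Report protein intake from all collections and again from complete ones, with the nitrogen-to-creatinine ratio as a check. Showing both guards against the rule itself removing more samples from one arm than another.

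The cost is one inexpensive assay on urine already in hand and a few lines on a form. The downside is that some collections will be set aside as incomplete.
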